Study Design Overview and Methodology	
This is a 180-day, prospective, evaluator-blind, multicenter, staged, confirmatory study designed to evaluate the safety and effectiveness of the Octave System in treating the brow, face, and neck to lift the eyebrow and to improve the appearance of the face and neck.
 
All enrolled healthy, adult subjects will receive a single Octave-Ultherapy treatment of the brow, face, and neck. In Stage 1, an initial cohort of 10 subjects will be treated with one transducer at energy level 4 CCI [REDACTED] and one transducer at energy level 2 CCI [REDACTED]. In Stage 2, the remaining subjects will be treated with three transducers at energy level 4 CCI [REDACTED] and one transducer at energy level 2 CCI [REDACTED]. The majority of subjects will be followed for 180 days; only those Stage 1 subjects who do not reconsent for extended participation will be followed for 90 days, and photographs will be taken at baseline, Day 90, and Day 180.
 
For the primary endpoint, the proportion of subjects with eyebrow lift will be determined by a blinded, independent assessment of photographs at 90 days post-treatment compared to baseline. The same photograph comparison will be made at 180 days post-treatment, as a secondary endpoint. To reduce potential bias associated with evaluating only treated-subject photographs, images of untreated individuals, collected at two time points, will also be included for blinded, independent photographic review. Secondary effectiveness evaluations will also include quantitative measurement of eyebrow lift and three FACE-Q modules (i.e., Satisfaction with Forehead and Eyebrows; Satisfaction with Lower Face and Jawline, and Patient-perceived Age VAS).
 
Study subjects will have approximately 4 on-site study visits, including screening, baseline/treatment, a Day 90 (\pm 7 days) post-treatment visit, and a Day 180 (\pm 14 days) post-treatment visit. Follow-up telephone calls will occur at 3 days (\pm 1 day), 14 days (\pm 3 days), 28 days (+ 3 days), 120 days (\pm 7 days), and 150 days (\pm 7 days) after Octave-Ultherapy treatment.
 
Expected study duration is approximately 8 months from screening of the first subject until final follow-up of the last subject. In Stage 1, an initial cohort of 10 subjects will be enrolled, safety data will be assessed to Day 14, and subjects will participate until study end at Day 90 or Day 180 if reconsented for extended participation. In Stage 2, all enrolled subjects will participate until study end at Day 180. The planned duration of participation for individual subjects is up to 30 weeks, including up to 21 days for screening, 1 day for treatment, and 90 or 180 days for follow-up.

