13.1 Estimation of Sample Size

A responder rate of 72% is assumed for the proportion of subjects with eyebrow lift from baseline to Day 90, as defined by the correct selection of the Day 90 standardized, photographic images by two of three independent, blinded evaluators in the previous Ulthera System eyebrow clearance study **CCI** [REDACTED] Monte-Carlo simulations were conducted to obtain sample sizes of evaluable subjects required to achieve an improvement rate (i.e., eyebrow lift reported by two of three independent, blinded evaluators) of $\geq 65\%$ and lower bound of 1-sided 95% confidence interval above 50%. To achieve this threshold with $\geq 85\%$ power, a sample size of 40 evaluable subjects will be required. Assuming a maximum attrition of 10 subjects, approximately 50 subjects will be enrolled. In Stage 1, 10 subjects will be enrolled, while all other subjects will be enrolled in Stage 2. Because a sample size of 40 subjects who complete the full Ultherapy treatment session is required, study enrollment will continue until the required number of treated subjects is achieved.

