## 2 Clinical Trial Design and Objectives

### 2.1 Clinical Study Design

This is a 180-day, prospective, evaluator-blind, multicenter, staged, confirmatory study designed to evaluate the safety and effectiveness of the Octave System in lifting the brow and improving the appearance of the face and neck. Approximately 50 subjects will be enrolled at up to five investigational sites in the United States.

All Fitzpatrick skin types (FST) will be eligible for study enrollment. It is estimated that approximately 85% of the total sample size will consist of subjects with a FST I, II, or III, and approximately 15% of subjects will be FST IV, V, or VI. Subjects enrolled will be healthy male or female subjects, aged 35 to 65 years at the time of screening, with mild to moderate eyebrow/upper-face laxity and fine lines, wrinkles, and laxity of the mid- to lower face and neck that are amenable to improvement with non-invasive intervention and are not severe enough for surgical intervention.

In this non-comparative, staged, confirmatory study, investigators and subjects will not be blinded to treatment, subjects will not be randomized, and all enrolled subjects will receive a single Octave-Ultherapy treatment of the brow, upper, mid, and lower face, and neck. Subjects in Stage 1 (n = 10) will receive treatment with one transducer **CCI** at energy level 4 and one transducer **CCI** at energy level 2. Remaining subjects in Stage 2 will receive treatment with three transducers **CCI** at energy level 4 and one transducer **CCI** at energy level 2. In Stage 1, an initial cohort of subjects will be enrolled, safety data will be assessed to Day 14, and subjects will participate until study end at Day 90 or Day 180 if reconsented for extended participation. In Stage 2, all enrolled subjects will be followed for 180 days. In addition, to reduce potential bias associated with using only treated-subject photographs for evaluation, photographs of approximately 25 untreated individuals, who meet selected appearance criteria, will be collected at two different time points and subsequently paired for evaluation by the independent, blinded

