## 3 Determination of Sample Size

A responder rate of 72% is assumed for the proportion of subjects with eyebrow lift from baseline to Day 90, as defined by the correct selection of the Day 90 standardized, photographic images by two of three independent, blinded evaluators in the previous Ulthera System eyebrow clearance study (K072505). Monte-Carlo simulations were conducted to obtain sample sizes of evaluable subjects required to achieve an improvement rate (i.e., eyebrow lift reported by two of three independent, blinded evaluators) of  $\geq$  65% and lower bound of 1-sided 95% confidence interval (CI) above 50%. To achieve this threshold with  $\geq$  85% power, a sample size of 40 evaluable subjects will be required. Assuming a maximum attrition of 10 subjects, approximately 50 subjects will be enrolled. In Stage 1, 10 subjects will be enrolled, while all other subjects will be enrolled in Stage 2. Because a sample size of 40 subjects who complete the full Ultherapy treatment session is required, study enrollment will continue until the required number of treated subjects is achieved.

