#### 6.1.1 Primary Effectiveness Endpoint

##### 6.1.1.1 Primary analysis

The primary endpoint of the study is the proportion of treated subjects with eyebrow lift by comparing photographs taken at Day 90 (post-treatment) with baseline (pre-treatment) photographs.

Each independent evaluator will assess “Eyebrow Lift”, “No Eyebrow Lift” or “Cannot Evaluate” between Photograph 1 (baseline) and Photograph 2 (post-baseline). Photograph 1 will be identified, and the independent evaluators will be blinded to the random distribution of treated versus untreated status of the comparator Photograph 2 (i.e., Day 90 post-treatment among treated subjects or post-baseline for untreated individuals). Lift will be declared if at least two blinded evaluators indicate “Eyebrow Lift” for the comparator photograph. In case at least two evaluators declare a photograph as not assessable (i.e., “Cannot Evaluate” is ticked), the corresponding lift score over all evaluators will be set to missing for the primary analysis. In case one evaluator rates a photograph as “Cannot Evaluate” and the other two evaluators disagree, the overall lift score will be set to “No Lift”.

The point estimate for the proportion of subjects fulfilling the primary endpoint will be described by frequency statistics for the ITT subset.

[figure not shown]
Effectiveness is established if:

[figure not shown]
- A. the point estimate is  $\geq 65\%$  and
- B. the lower bound of the one-sided 95% Wilson CI is  $> 50\%$ .

In addition, the proportion of untreated individuals fulfilling the primary endpoint will be calculated. It is expected that the point estimate for the proportion of untreated individuals is  $< 50\%$ .

Missing data, including a missing primary endpoint assessment in subjects with unacceptable (i.e. unassessable) or missing photographs at baseline or Day 90, will be imputed by multiple imputation. In case of complete data, no multiple imputation will be performed and the primary analysis is based on complete data for the ITT.

Imputation is done 50 times using a fully conditional specification logistic regression method, as implemented in SAS PROC MI with statement FCS LOGISTIC, and will use the investigational site and the baseline characteristics age and BMI as independent variables.

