In a first step a total of  $m=50$  imputed datasets will be generated, where missing data in the primary endpoint (lift over all evaluators) is modelled via logistic regression based on input variables site, age and BMI at baseline. 

  response is coded as ("no lift", "lift"). The lower bound of the one-sided 95% Wilson CI ([WL, WU]) will be calculated using the following steps, as detailed in [1]:

1. The mean sample response  $\hat{p}_{Imp}$  and sample variance  $\hat{U}_{Imp}$ ,

$$\hat{U}_{Imp} = \frac{\hat{p}_{Imp} (1 - \hat{p}_{Imp})}{n},$$

will be calculated for each of the  $m=50$  imputed datasets with sample size  $n$ .

2. The overall mean  $\bar{p}_m$  and variance  $\bar{U}_m$  over all imputed datasets will be calculated:

$$\bar{p}_m = \frac{1}{m} \sum_{Imp=1}^m \hat{p}_{Imp},$$

$$\bar{U}_m = \frac{1}{m} \sum_{Imp=1}^m \hat{U}_{Imp}.$$

These will be used to obtain  $B_m$ ,

$$B_m = \frac{1}{m-1} \sum_{Imp=1}^m (\hat{p}_{Imp} - \bar{p}_m)^2,$$

the between-sample variance.

3. The lower boundary of the one-sided 95% Wilson CI (WL and WU) will be calculated as

$$\left[ \frac{2\bar{p}_m + \frac{t^2}{n} + \frac{t^2 r_m}{n}}{2 \left( 1 + \frac{t^2}{n} + \frac{t^2 r_m}{n} \right)} - \sqrt{\frac{\left( 2\bar{p}_m + \frac{t^2}{n} + \frac{t^2 r_m}{n} \right)^2}{4 \left( 1 + \frac{t^2}{n} + \frac{t^2 r_m}{n} \right)^2} - \frac{\bar{p}_m^2}{1 + \frac{t^2}{n} + \frac{t^2 r_m}{n}}} \right],$$

where  $t$  denotes the 0.95 quantile of the t-distribution with degrees of freedom  $\nu$ ,

$$\nu = (m - 1) \left( 1 + \frac{1}{r_m} \right),$$

and with

$$r_m = \left( 1 + \frac{1}{m} \right) \frac{B_m}{U_m}.$$

The study is considered successful, and consequently effectiveness is established, if the parameter estimate  $\bar{p}_m \geq 65\%$  (condition A), and the lower limit of the one-sided 95% Wilson CI exceeds the margin of 50% (condition B).

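### The primary-endpoint imputation model leaves out treatment stage, which biases the lift estimate only if lift rate and Day 90 missingness both differ by stage

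*SAP*

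**What the plan says.** SAP 6.1.1.1 names the imputation covariates twice in plain text. The FCS LOGISTIC model "will use the investigational site and the baseline characteristics age and BMI as independent variables", and the outcome "is modelled via logistic regression based on input variables site, age and BMI at baseline". SAP 6.4.5 adds only that the smallest sites are merged if the model does not converge.

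The stages differ in treatment. Under the Protocol synopsis, "an initial cohort of 10 subjects will be treated with one transducer at energy level 4", plus one at level 2. "In Stage 2, the remaining subjects will be treated with three transducers at energy level 4", again plus one at level 2. SAP 2.1 agrees: "Remaining subjects in Stage 2 will receive treatment with three transducers" at level 4. On numbers, SAP 3 says "In Stage 1, 10 subjects will be enrolled, while all other subjects will be enrolled in Stage 2", so with about 50 enrolled the split is 10 to about 40.

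The primary analysis pools both stages. The sensitivity analyses in SAP 6.1.1.2 and the subgroups in 6.1.1.3 (BMI change, age, baseline BMI, site) do not use stage. Success needs an estimate of at least 65% (condition A) and a one-sided 95% Wilson lower limit above 50% (condition B).

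**The concern.** An imputation model should contain the recorded variables that may predict both the outcome and whether it is missing. Stage is known for every subject and defines the treatment received. Without it, a missing Stage 1 outcome is drawn largely from four-transducer results, and a missing Stage 2 outcome partly from two-transducer results, except where site stands in for stage.

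At stake is a point-estimate threshold. With 50 subjects, condition A is the binding one and one subject is worth 2 points. The multiply imputed estimate averages 50 data sets, so it can fall anywhere between the whole-subject steps, and a shift of a point can decide a result close to 65%.

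**Working it through.** **Inputs from the documents.** 10 Stage 1 and about 40 Stage 2 subjects; maximum attrition 10 of 50; 50 imputations; cut-offs 65% and 50%; Stage 1 at two to five sites (Protocol 9.1). SAP 3 assumes one rate for everyone: "A responder rate of 72% is assumed for the proportion of subjects with eyebrow lift from baseline to Day 90".

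**Inputs that must be assumed.** The lift rate in each stage and the Day 90 missingness in each stage.

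**1. The plan's own figure.** Protocol 13.1 says "a sample size of 40 evaluable subjects will be required" for at least 85% power. At n = 40 the rule is at least 26 responders (26/40 = 65.0%, Wilson lower limit 52.0%). Exact power at 72% is 87.6% and type I error at 50% is 4.0%. The stated figure is reproduced.

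**2. Which condition binds at 50.** Condition A needs 0.65 × 50 = 32.5, so 33 responders (66%); 32 (64%) fails. Condition B alone needs 31.

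**3. Closed-form shift.** Let m1 and m2 be the numbers missing in Stages 1 and 2, o1 = 10 − m1, o2 = 40 − m2, o = o1 + o2, and D the Stage 2 lift rate minus the Stage 1 rate, in points. Pooled imputation fills each gap at the observed mix, so a missing Stage 1 subject is overstated by (o2/o)·D and a missing Stage 2 subject understated by (o1/o)·D. Hence

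shift = [m1·(o2/o) − m2·(o1/o)] · D / 50.

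It is zero if D = 0 or if m1/o1 = m2/o2, that is, if both stages have the same missing rate.

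**4. Simulation.** Logistic imputation on site, age and BMI, with and without stage; n = 50; five sites, Stage 1 at two of them; 50 imputations; a light penalty against separation. The 27.5-point gap is 50% against 77.5% (0.2 × 50 + 0.8 × 77.5 = 72%); the 12.5-point gap is 62% against 74.5%. Bias is measured against the full-data proportion; ranges reflect repeat runs.

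| Missing, Stage 1 / Stage 2 | D | Closed-form shift | Bias without stage | Bias with stage | Due to omission |
|---|---|---|---|---|---|
| 3 / 0 | 27.5 | 3 × (40/47) × 27.5/50 = +1.4 | +1.1 | 0.0 to +0.2 | about +1 |
| 5 / 0 | 27.5 | 5 × (40/45) × 27.5/50 = +2.4 | +1.9 to +2.0 | +0.1 to +0.2 | about +1.8 |
| 0 / 10 | 27.5 | −10 × (10/40) × 27.5/50 = −1.4 | −1.9 to −1.8 | −1.0 to −0.9 | about −0.9 |
| 3 / 0 | 12.5 | 3 × (40/47) × 12.5/50 = +0.6 | +0.3 | −0.1 to −0.2 | about +0.5 |
| 2 / 8 | any | 2 × (32/40) − 8 × (8/40) = 0 | same in both | same in both | 0 |

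The simulated shifts are smaller than the closed form because site absorbs part of the stage effect. In the 0 / 10 case about half of the total bias remains with stage in the model, so it is not due to the omission. More extreme inputs give more: 5 / 0 with D = 40 gives 5 × (40/45) × 40/50 = +3.6 in closed form.

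**5. Effect near the cut-off.** With 40% in Stage 1 and 70% in Stage 2 (0.2 × 40 + 0.8 × 70 = 64% overall) and 3 of 10 Stage 1 subjects missing, the chance of an estimate of at least 65% is 44% with complete data, 45% with stage in the model and 52% without.

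**6. Cost of adding stage.** If lift is 72% in both stages, RMSE without and with stage is 3.45 and 3.49 points (2 of 10 and 8 of 40 missing), or 3.41 and 3.60 (5 of 10 and 5 of 40 missing). At the 12.5-point gap with 3 of 10 missing it is 1.91 and 2.03, so there is no RMSE gain. Separation is a real risk: with 5 Stage 1 subjects observed at a 72% rate, all share one outcome with probability 0.72^5 + 0.28^5 = 0.193 + 0.002, about 20%.

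**The case against.** The strongest objection is that the harm needs two conditions, and the documents establish neither. They give one lift rate, no rate by stage and no missingness by stage. With equal missing rates the two models agree at any gap, and the larger shifts above need a wide gap together with very uneven losses. This stands, and it is why the point is conditional.

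A reader might infer that missingness must differ by stage because Stage 1 consented to 90 days and Stage 2 to 180. The documents do not support that. Day 90 lies within both consent periods, and reconsent is requested at the Day 90 visit itself (Protocol 9.1 and 11.1), so declining it cannot remove the Day 90 photograph. At Day 180, Stage 1 subjects without reconsent are outside the assessed set (SAP 6.1.2) and are not imputed. Other routes are possible but unquantified. The stages run one after the other, and SAP 6 foresees on-site visits missed because of COVID-19. Protocol 10.5.3 has subjects who stop for intolerable pain followed for safety only, whereas 9.2.6.1 asks subjects who discontinue treatment to complete all remaining visits. Those two passages should be reconciled, since they decide whether such a subject contributes a Day 90 photograph.

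A reader might also take the 52% against 45% as inflated type I error. It is not: the tested margin is 50%, and 64% was chosen because it lies just below the cut-off.

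The worst-case analysis in SAP 6.1.1.2 (missing counted as no lift) does test the direction that favours the sponsor. The observed-case analyses give less protection, because they carry the same shift in stage mix. Site is a partial proxy only: nothing in the documents keeps Stage 1 sites from enrolling in Stage 2, and merging sites under SAP 6.4.5 weakens it further.

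Finally, an extra term could overload the model. The RMSE cost is small, but it was obtained with a penalised fit, and the visible SAP text specifies no penalty. This part of the objection stands and shapes the fix.

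**Conclusion.** The omission is plain in the text; its effect is conditional. Bias arises only if lift rate and Day 90 missingness both differ by stage, given site, age and BMI. It would go too far to say that the estimate is off by 1 to 2 points, or always in the sponsor's favour.

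Under the assumed 27.5-point gap, losses mainly in Stage 1 move the estimate up by about 1 to 2 points, and losing 10 Stage 2 subjects moves it down by about 0.9, which is conservative. With the smaller gap and 3 Stage 1 subjects missing the shift is about 0.5 points, a quarter of one subject. All of these rest on assumed stage rates and missingness, 50 subjects and Stage 1 at two of five sites; if stage were unrelated to site, the shifts would be closer to the closed form. They affect the conclusion only if the result lands close to 65%. This is a worthwhile, inexpensive improvement and does not invalidate the primary analysis.

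**What to change.** - In SAP 6.1.1.1, add stage (1 or 2) as a binary covariate in the FCS LOGISTIC model. Carry it by reference into the Day 180 imputation (6.1.2) and the image-quality imputation analysis (6.1.1.2).
- Extend SAP 6.4.5 with an ordered fallback if stage separates or the model does not converge: merge sites first, then use a penalised or augmented fit, then drop stage and report that this was done.
- Tabulate the primary endpoint, including the number missing, by stage, so that a reader can see whether either condition for bias is present.

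The cost is one covariate in the code, a few SAP sentences and one table. The downside is one more parameter: RMSE up to about 0.2 points larger if stage turns out to be irrelevant, and a separation risk with only 10 Stage 1 subjects, which the fallback covers. The change should be made before the Day 90 database close.

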13.4.1.1 Primary Effectiveness Endpoint

The proportion of subjects fulfilling the primary endpoint will be described by frequency statistics for the ITT subset.

Effectiveness is established if the point estimate is $\geq 65\%$ and the lower bound of the one-sided 95% Wilson CI is $> 50\%$.

In addition, the proportion of untreated individuals fulfilling the primary endpoint will be calculated. It is expected that the point estimate for the proportion of untreated individuals is $< 50\%$.

[figure not shown]

Sensitivity analyses will comprise:

- PP population with observed cases,
- ITT with observed cases, and

- ITT with missing value treated as no eyebrow lift.

CCI

Gain or loss of ≥ 2 BMI units from screening to Day 90 will be considered a major protocol deviation. Subjects with gain or loss of ≥ 2 BMI units from screening to Day 90 will be excluded from PP population. The following subgroups will be defined by the change in body weight from screening to Day 90:

- Subjects in ITT population with gain of ≥ 2 BMI units;
- Subjects in ITT population with loss of ≥ 2 BMI units; and
- Subjects in ITT population with change of < 2 BMI units.

Primary endpoint with observed cases will be analyzed in all subgroups, as defined above, with more than five subjects.

[figure not shown]

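### As printed, the SAP's degrees of freedom for the multiply imputed Wilson bound lack a square, so the primary lower bound is slightly too low when outcomes are missing

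*SAP*

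**What the plan says.** SAP 6.1.1.1 sets two conditions for success at Day 90: A, a point estimate of at least 65%, and B, that "the lower bound of the one-sided 95% Wilson CI is" above 50%. Protocol 13.4.1.1 states the same rule.

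Missing outcomes are multiply imputed: "Imputation is done 50 times using a fully conditional specification logistic regression method". The SAP then defines the mean within-imputation variance Ū, the between-imputation variance B and the ratio r = (1 + 1/m)B/U, where the U is printed without its bar. The multiplier t in the bound "denotes the 0.95 quantile of the t-distribution with degrees of freedom" ν, printed as ν = (m − 1)(1 + 1/r). For these steps the SAP refers to its reference [1], a paper on Wilson intervals with multiple imputation.

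The formula is conditional: "In case of complete data, no multiple imputation will be performed". The same method is reused for the Day 180 photographic endpoint (SAP 6.1.2) and for the imputed version of the image-quality sensitivity analysis (SAP 6.1.1.2).

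**The concern.** The usual degrees of freedom for a multiply imputed estimate carry a square on (1 + 1/r), and the printed formula has none. The formula supplies the multiplier in the bound that decides condition B, so this is a fault in the specification of the primary success rule. A programmer who follows the printed text and a checker who uses the standard result would obtain different multipliers and slightly different bounds for the trial's main result.

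**Working it through.** **Inputs.** From the SAP: m = 50, one-sided 95%, margins of 65% and 50%, about 50 enrolled, at most 10 lost, 40 evaluable. Assumed, because the documents give no value: r from 0.01 to 1.0.

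**The plan's own figure.** SAP 3 states: "A responder rate of 72% is assumed". With complete data and the ordinary Wilson bound (z = 1.645), 40 subjects need at least 26 responders. The exact power at 72% is 87.6% and the exact type I error at 50% is 4.03%. This agrees with the stated power of at least 85% for 40 evaluable subjects. The degrees of freedom play no part in it.

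**Degrees of freedom from the SAP's quantities.**
1. Total variance: T = Ū + (1 + 1/m)B = Ū(1 + r).
2. With Ū taken as fixed and B on m − 1 degrees of freedom, the variance of T is (1 + 1/m)² × 2B²/(m − 1).
3. Setting this equal to 2T²/ν gives ν = (m − 1)T²/[(1 + 1/m)B]².
4. Since (1 + 1/m)B = rŪ, this is (m − 1)[(1 + r)/r]² = (m − 1)(1 + 1/r)².

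The printed ν is therefore too small by a factor of 1 + 1/r: 21-fold at r = 0.05 and 5-fold at r = 0.25.

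**The rest of the bound.** Write a = t²(1 + r)/n. Solving (p̄ − p)² = t²p(1 − p)(1 + r)/n for its lower root gives (2p̄ + a)/[2(1 + a)] − √{(2p̄ + a)²/[4(1 + a)²] − p̄²/(1 + a)}. This is the SAP's expression, so only ν departs from the derivation.

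**Numbers at n = 50, p̄ = 0.65, m = 50.**

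| r (assumed) | ν printed | ν squared | Bound, printed | Bound, squared |
|---|---|---|---|---|
| 0.05 | 1,029 | 21,609 | 53.09% | 53.10% |
| 0.11 | 494.5 | 4,989.5 | 52.74% | 52.76% |
| 0.25 | 245 | 1,225 | 51.96% | 52.00% |
| 1.0 | 98 | 196 | 48.40% | 48.48% |

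Worked line for r = 0.25: printed ν = 49 × 5 = 245 and t = 1.6511; squared ν = 49 × 25 = 1,225 and t = 1.6461. Then a = 1.6511² × 1.25/50 = 0.0682 gives 51.96%, and a = 1.6461² × 1.25/50 = 0.0677 gives 52.00%.

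Over n = 40 and 50, p̄ = 0.62 to 0.72 and r = 0.01 to 1.0, the difference runs from 0.002 to 0.09 percentage points, always in the same direction.

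**Effect on the decision.** At p̄ = 0.65 and n = 50, the two bounds lie on opposite sides of 50% only for r between about 0.639 and 0.653. If the ITT population held only 40 subjects, the window would be about 0.318 to 0.328.

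The full rule was simulated with n = 50, m = 50, imputation without covariates and 40,000 trials per scenario, at true rates of 50%, 65% and 72%.

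| Missing of 50 | Mean r | Trials in which the decision changed |
|---|---|---|
| 3 | 0.06 | 0 |
| 5 | 0.11 | 0 |
| 10 | 0.25 | 0 |
| 15 | 0.43 | 1 to 3 |
| 20 | 0.66 to 0.67 | 12 to 59 |

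With 3 to 10 missing, condition B taken alone changed in 14 to 111 of 40,000 trials, but the overall decision did not change in any of them. With 10 missing, the 95th percentile of r was at most 0.337, well below 0.639.

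**The case against.** The strongest reply is that the square may have been lost when the PDF was read. The other squares in the same derivation survive, which counts against this. However, the very next equation shows U without its bar, although the SAP defines only the barred mean and the per-dataset variance. Either the reading or the SAP dropped that mark, and the text cannot show which. The point therefore concerns the formula as printed here and needs confirming on the original page.

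Three stronger readings are tempting, and the documents do not support them.
- **That the program computes the wrong bound.** The imputation code is not shown, so what was programmed is unknown. Nor can one say that reference [1] was miscopied, because it is not available; the squared form rests on the SAP's own components.
- **That all Day 90 and Day 180 results are affected.** With complete data the primary analysis uses no imputation. The observed-case and worst-case sensitivity analyses do not use the formula either.
- **That a false success could result.** Because 1 + 1/r exceeds 1, the printed ν is always too small and the bound always too low.

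It is also fair to say that the effect may not show. SAP 6 reports percentages to one decimal, so 51.96% and 52.00% both print as 52.0%. At other values the last digit differs: 52.7% against 52.8% at r = 0.11.

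What stands is that the printed rule disagrees with its own variance components.

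**Conclusion.** As printed, the degrees of freedom should be (m − 1)(1 + 1/r)² and are not. When outcomes are missing, the lower bound is too low by less than 0.1 percentage point for assumed r up to 1.0. A change of decision is possible in principle, but at n = 50 and 65% it needs r near 0.64 to 0.65, against about 0.25 for the planned maximum of 10 of 50 missing. The conclusion assumes that the page was read correctly. The size depends on the assumed r and, for the decision, on a simulation without the site, age and BMI covariates of the SAP's imputation model. This is a minor correction, and the sample size is unaffected.

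**What to change.** Check the original SAP page and the program. If the square is absent, make these changes in SAP 6.1.1.1:
- Write ν = (m − 1)(1 + 1/r)².
- Use the mean within-imputation variance, with its bar, in the definition of r.
- State that t is the normal 0.95 quantile (1.645) if B = 0. In that case 1/r is undefined, and the SAP's exemption covers only complete data.
- Align the program, including its use for Day 180 and for the image-quality analysis.

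The cost is one exponent, one bar and one sentence in the SAP, and a short check of the code. No new data and no change in sample size are needed.
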